Incisional negative pressure wound therapy for preoperatively irradiated pelvis and lower extremity soft tissue sarcoma wounds. A prospective, randomized pilot trial.

NCT02638298

Date Last Modified: April 21st, 2023

Principal investigator

[name]., MSCR

Associate [name]
Orthopaedic Oncology
Director of Orthopaedic Research
Associate Program Director
Medical University of South Carolina

[name]
[name]
[contact]
[contact]

Table of Contents

Hypothesis/Specific Aims.....	3
Background and Significance.....	3-5
Research Design.....	5-8
Methods.....	8-10
Budget.....	11-12
References.....	13

**Medical University of South Carolina
Protocol
PI Name: [name], MSCR**

Study Title: Incisional negative pressure wound therapy for preoperatively irradiated pelvis and lower extremity soft tissue sarcoma wounds. A prospective, randomized pilot trial.

A. HYPOTHESIS/SPECIFIC AIMS

The hypothesis of the proposed study is that use of a negative pressure wound therapy (NPWT) dressing on preoperatively radiated pelvic and lower extremity soft tissue sarcoma surgical wounds will significantly reduce the incidence and cost of wound complications.

This hypothesis will be tested through accomplishing the following specific aims:

- 1) Specific Aim 1- To estimate the wound complication rate of post-operative negative pressure dressings and traditional dry dressings, and risk of secondary interventions after resection of soft tissue sarcoma in lower extremities and the pelvis that have received pre-operative radiation. Wound complications are defined as a superficial infection, deep infection, need for prolonged (> 3 weeks) wound packing, or return to the operating room within six months for a secondary procedure. A secondary analysis of frequency and likelihood of antibiotic usage, pain scores, and functional scores will be analyzed in each group.
- 2) Specific Aim 2- To estimate the total cost of care and resource utilization in patients treated with negative pressure wound therapy and traditional dry dressings.

B. BACKGROUND AND SIGNIFICANCE

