Each patient will undergo the appropriate standard of care surgical procedure regardless of which treatment arm they are randomized to. This study will not affect any of the surgical decision making or surgical technique utilized. After skin closure from the surgical procedure patients will receive either a NPWT dressing or dry gauze dressing depending on the randomization.

Postoperative Care:

Postoperative care will be identical for both treatments. Wound care instructions will be given to both groups of study patients. Instructions for the control (dry gauze) group will be within the standard of care for each surgeon’s practice. Typically, a standard dressing care involves a dressing change at post-operative day two and then daily for the next week or until the wound is dry. Standardized instructions for the NPWT will be given in concordance with manufacturer’s recommendations. The NPWT dressing

would be typically discontinued on postoperative day 5-7 and standard dry gauze will be implemented at that point as needed. The Prevena™ device is FDA approved for use on incisions.

Physical therapy will be initiated prior to discharge, and continue either at home or as an outpatient, and continued at the discretion of the therapist and treating physician and in accordance with standard practice.

Postoperative Evaluations:

Formal wound and outcome assessments will take place at the 2 week, 6 week, 3 month and 6 month visits postoperatively or if patient presents for an unscheduled office visit with a wound complaint. Some information will be gathered from the medical record such as medication usage, information about the tumor from the pathology report, days in the hospital, treatment history of the tumor, and complications. Postoperative visits, and will include recording VAS pain levels, tumor size, margin status, length of hospitalization, use of pain medicines, and functional scoring. A wound assessment will be done as well.

Wound Assessment-

Direct assessment of each participant wound will be made during the specified follow up period at 2 weeks, 6 weeks, 3 months, and 6 months postoperatively.

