Risks Associated With NPWT Therapy/Dressing

Risks Due to PREVENA™ Incision Management System

Risks	Disorders/Conditions
Skin and Subcutaneous Tissue	
• Local cutaneous reaction (i.e. redness, rash, significant pruritis, urticaria)• allergic reaction• maceration• minor soft tissue damage• epidermal (skin) stripping• minor bleeding• pain• contusion (bruising)
Other	
• bleeding complications (associated with the surgical procedure, concomitant therapies and co-morbidities)• first degree burn (if device gets warm)• exposure related infection• localized infection• physical discomfort• minor desiccation (due to dressing leak)• moderate soft tissue damage (i.e. due to trip hazard, tubing entanglement)• deterioration of the wound (due to lack of visibility of incision site through dressing)

E. METHODS

Table 2

ASSESSMENT Provena™ 1 week duration	PRE-OP	2 WEEK POST OP VISIT	6 WEEK POST OP VIST	3 MONTH POST OP VISIT	6 MONTH POST OP VISIT
Wound assessment		X	X	X	X
Tumor size (cm)		X			
Type and Dose of Radiation	X				
Margin (+/-)		X			
Pain (VAS)	X	X	X	X	X
Hospitalization (days)		X			
Narcotic usage (+/-)	X	X	X	X	X
MSTS score			X	X	X
PROMIS Global Health	X			X	X

Other data collected to be analyzed for an association with wound complications or impact on treatment effect of Prevena™ (table 2)-

- 1) Surgery associated wound healing factors- prolonged (>3 wks) drainage, need for prolonged dressing changes or wound packing (>3 wks), return to OR, and use of antibiotics- All visits
- 2) Size of the tumor resected (cm)-2 week visit
- 3) Development of postoperative hematoma or seroma- All visits
- 4) Patient comorbidities- Smoking, peripheral vascular disease, BMI, diabetes, and MRSA status
- 5) Pain: The subject will be asked to record their current level of leg pain, and level of pain with leg use on a visual analogue scale (VAS) at all visits
- 6) Length of hospitalization (days)-2 week visit
- 7) Duration of narcotic usage (days)-All visits
- 8) Physical Function: The subject will be asked to complete a MSTS score, a validated patient survey for assessment of function at the 6 week, 12 week, and 6 month
- 9) Patient Global Assessment: The subject will be asked to complete a PROMIS Global Health forma validated patient survey for assessment of global musculoskeletal health and wellbeing at the preoperative visit, 3 month and 6 month visits.

Adverse Events:

Definitions

Adverse Event (AE).

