Analytic Approaches: To assess specific aim one patients will be followed longitudinally for the development of a wound complication and incidence of secondary procedures. Criteria for a wound complication are listed above. The data will be collected prospectively during routine follow up care of the patient and will include presence of absence of wound complication. The proportion of patients with a wound complication will be estimated and the 95% confidence for the true wound complication rate will be calculated with an exact binomial procedure. Although it is not the primary analysis, we will also compare the complication rates across the two groups using a Fisher's exact test (although the study is underpowered for this analysis). We will also use a logistic regression analysis where we adjust for center (using indicator variables) to estimate the overall wound complication rate in each group. For the risk of secondary interventions, the incidence of procedures performed for wound complications will be collected and multiple logistic regression analysis will be used to adjust these procedures in the incidence of wound complications.

To assess specific aim two the total cost of perioperative and post-operative care will be estimated from hospital billing records for patients. The median cost for the NPWT group and control group will be estimated and compared with independent t-test for normally distributed data and the Mann-Whitney test for any nonparametric data. A post hoc analysis of the cost of treatment for each arm will provide comparative effectiveness data for the use of NPWT in preoperatively radiated sarcoma surgical wounds. This is come directly from hospital and clinic charges, dressing and medication costs, and direct societal cost estimates from time missed from work.

Sample size justification: This is a pilot study with the primary objective of estimating complication rates in our patient population using NPWT and traditional dry dressings. We estimate that each of four institutions can enroll a least 40 patients over 36 months for a total of 160 patients. Assuming up to 5 patients in each group will have inevaluable data or follow-up, we plan on a total of 75 evaluable patients in each group. With 75 patients in each group and assuming complication rates of 10% to 30%, we have the following $\frac{1}{2}$ widths for 95% confidence intervals.

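### Aim 2 costs work loss that no form collects, sets charges beside costs with no common valuation basis, and schedules hospital days only at 2 weeks

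*Combined protocol and SAP*

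**What the plan says.** The Combined protocol and SAP has two specific aims. The second (section A) is "To estimate the total cost of care and resource utilization in patients treated with negative pressure wound therapy and traditional dry dressings".

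Under Analytic Approaches, the plan first states that "the total cost of perioperative and post-operative care will be estimated from hospital billing records for patients". It gives no closing date for that period. The comparison follows: "The median cost for the NPWT group and control group will be estimated and compared with independent t-test for normally distributed data", with a Mann-Whitney test as the alternative.

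A further analysis is then announced: "A post hoc analysis of the cost of treatment for each arm will provide comparative effectiveness data". The next sentence gives its ingredients: "This is come directly from hospital and clinic charges, dressing and medication costs, and direct societal cost estimates from time missed from work".

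On data collection, section E lists "Length of hospitalization (days)-2 week visit", and Table 2 agrees, with a single mark for hospitalization at that visit. Postoperative Evaluations (section D) describes the source differently: "Some information will be gathered from the medical record such as medication usage, information about the tumor from the pathology report, days in the hospital". No time limit is attached there.

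**The concern.** Cost is part of the trial's hypothesis and the subject of one of its two aims. The economic question is whether the price of the device is offset by less care for wound complications. The answer depends on three things: each ingredient must be observed, all ingredients must be valued on one scale, and they must cover the period in which complications count.

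The plan is open to doubt on all three. One ingredient has no data item. Two others are named in different currencies, charges and costs. The only scheduled measure of inpatient use ends long before the six-month complication window does. If this stays unresolved, the sites will have to settle it after the data are in, perhaps each in its own way, and the work-loss part would have to be abandoned or rebuilt from patients' memory.

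**Working it through.** The documents contain no cost value, cost-to-charge ratio or precision statement for Aim 2, so there is no planned figure to reproduce. The check is a comparison of sections, with two small calculations to give scale.

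**1. Work loss: needed against collected**

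- Needed: time missed from work (Analytic Approaches, aim two).
- Preoperative Evaluation lists radiation, chemotherapy, pain, function and global health scores, comorbidities, tumor location and pain medicines. It has no work item.
- Postoperative Evaluations lists pain, tumor size, margins, length of stay, pain medicines, function and wound assessment, plus chart items. It has no work item.
- Table 2 and the nine-item list in section E have none either. The MSTS and PROMIS scores are described as measures of function and of health and wellbeing, not as counts of days missed.
- Billing records do not hold work absence.

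No listed source can supply this component.

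**2. Valuation basis**

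The ingredient list names charges for hospital and clinic care and costs for dressings and medication. No conversion is stated, and nothing says whether a dressing or drug already on the hospital bill is entered again.

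*Scale.* Let *r* be a hospital's cost-to-charge ratio. A charge of *C* represents a cost of *r* × *C*, so entering *C* unconverted beside items at cost overweights it by 1/*r*. The documents do not give *r*; the range below is an assumption.

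| Assumed *r* | Cost behind 1,000 of charges | Overweighting 1/*r* |
|---|---|---|
| 0.2 | 200 | 5.0 |
| 0.3 | 300 | 3.3 |
| 0.5 | 500 | 2.0 |
| 0.7 | 700 | 1.4 |
| 1.0 | 1,000 | 1.0 (no distortion) |

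*Double counting.* If a bill *B* already contains dressing *d* and drugs *m*, then *B* + *d* + *m* overstates the patient's total by *d* + *m*. The dressings differ between arms by design, so this error need not cancel: it adds *d*(NPWT) − *d*(gauze) to the arm difference, plus any difference in drug use.

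**3. Time window**

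- Return to the operating room counts as a complication up to six months (section A).
- Delayed infection is defined as beyond 6 weeks (Wound Assessment, section D).
- Hospital days are scheduled once, at 2 weeks (section E).
- Hospital days from the chart carry no limit (Postoperative Evaluations).
- Billing has no stated end date, and nothing says whether readmissions or care at non-study hospitals are included.

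Taking six months as 26 weeks, or 26 × 7 = 182 days, the scheduled item covers 14/182 = 7.7% of the window. This is calendar coverage of one data item. It is not the share of inpatient days lost, since the index stay falls early, and it is not a share of cost. The two sections on hospital days give different scopes and must be reconciled.

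**The case against.** Four points can be made for the plan.

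*Late care is not lost from the cost total.* A reader might infer from the 2-week item that total cost misses late complications. The documents do not support that. Cost is to come from billing records that include post-operative care, and the hospital-days item is nowhere named as a cost input. Return to the operating room, prolonged packing or dressing changes, and antibiotic use are recorded at all visits. Inpatient hospitalization is also a criterion for a serious adverse event, so readmissions are reportable. This objection stands. What remains is that the billing window has no end date and that the scheduled hospital-days item, the natural measure for the resource-utilization half of Aim 2, stops early.

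*Summing is not stated.* The plan lists charges, costs and societal estimates without saying that they are added or that charges stay unconverted. The list follows the analysis labelled post hoc, while the between-arm comparison is described from billing records alone. If the hospital bills the dressing, the dressing carries a mark-up too. All of this is fair, and it limits the point to an undefined valuation basis. The relation between the two analyses is itself unclear.

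*The comparison is partly protected.* A common mark-up on every component would leave a Mann-Whitney result unchanged, and block randomization by site roughly balances site-specific mark-ups between arms. This stands for bias between arms. It does not put charges and costs on one scale. The plan adjusts for center in the complication model and states no such adjustment for cost.

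*A break-even calculation is not planned.* A reader might turn the mark-up into an overstated break-even price for the device. That needs an assumed cost per complication and an assumed risk reduction, and it concerns means. The plan compares medians, and at its planning rates of 10% to 30% most patients in each arm have no complication. No break-even figure should be drawn.

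**Conclusion.** The point holds as a correctable gap in Aim 2.

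- Work loss is the firmest part. It rests on the text alone: the plan intends to cost it and has no item that records it.
- The valuation gap is real, but its size is unknown. The factor of about 1.4 to 5 depends entirely on assumed ratios of 0.2 to 0.7, and on charges being combined unconverted with items at cost, which the plan implies by aiming at a total but does not say.
- The window gap concerns inpatient days as a measure of resource use, and the absence of a closing date for billing. It does not show that late complications drop out of the cost total.

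The pilot's primary objective, estimating the complication rate in each arm, is unaffected. Because cost is one of two specific aims and the remedy is cheap, the plan should be changed.

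**What to change.** 1. Add days of work missed to each postoperative visit through 6 months, or remove the societal component from the analysis.
2. State one valuation basis. One way is to multiply each hospital's charges by its own cost-to-charge ratio before combining components, with unconverted charges as a secondary display. Count dressings and drugs already in the hospital bill once only. Say how the billing-record comparison and the post hoc cost analysis relate.
3. Replace the single 2-week hospitalization entry with cumulative inpatient days, including readmissions, to 6 months, and align Table 2, the section E list and Postoperative Evaluations. Use the same six-month window for billing, and state whether care at other hospitals is included.

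The cost is one ratio per hospital from its finance office, two short data items (one largely in the chart, one answered by the patient) and a few sentences of SAP text. Sample size, randomization and the primary analysis do not change.
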